- Must have a notable asymmetry in stance time (defined by a symmetry ratio of 0.90 or lower)

Exclusion Criteria:

- History of multiple strokes
- History of other neurological disease (e.g. Parkinson's Disease, Multiple Sclerosis)
- Uncontrolled medical conditions that would limit exercise tolerance (e.g. hypertension)
- Excessive spasticity in the paretic lower limb (score >3 on Modified Ashworth Scale)
- Contractures of the lower limb that prevent the ankle and knee from achieving a neutral position (sc

[figure not shown]
VI. Procedures

A. Informed Consent Process

Written consent forms with associated HIPAA forms will be prepared, approved by the institutional review board, and reviewed with each participant by a member of the research team prior to initiating study procedures. All participants will have the opportunity to ask any questions they may have, and a member of the research team will answer any questions posed. All participants will sign written informed consent and HIPAA forms prior to participating in any study related procedures. Participants will be given a copy of these signed forms for their personal record.

[figure not shown]
- Prior to initiating study procedures, participants will also complete a demographic form (Case Report Form (CRF_TPAD_Form_01)– See attached) and will be asked about use of an Ankle Foot Orthosis (AFO) – specifically if s/he typically ambulates inside the home with or without an AFO.
 - **IF** the participant typically **DOES NOT** wear the AFO for household ambulation, then the AFO **WILL NOT** be worn during the study procedures.
 - **IF** the participant typically **DOES** wear the AFO during household ambulation, then the AFO **WILL** be worn during the study procedures.

B. Overall Study Schema

Week 1 - PRE TEST (3 visits)	Week 2 - TRAINING (Daily visits)	Week 3 - FOLLOW UP (1 visit)
Consent **Day 1 only	10MWT with APDM® before and after training daily	10MWT with APDM®
Info Sheets **Day 1 only	Treadmill (TM) Training with Feedback	BBS
MoCA **Day 1 only	Overground Training	SIS
Stroke Impact Scale (SIS) **Day 1 only	Treadmill Assessments (Force Measures in tandem with baseline and post training gait on TM)	
10MWT with APDM®	BBS **Day 5 only	
Berg Balance Scale (BBS)	SIS **Day 5 only	

C. Assessments

i. Overground Assessments

Overground assessments will include:

- ✓ Gait Assessments
 - 10MWT as measured with APDM® sensors
- ✓ Balance Assessments
 - Berg Balance Scale (BBS)
- ✓ Self Assessments

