### ***2.2.2 Stance Time Symmetry Ratio***

Descriptive values (mean (SD)) of stance symmetry will be included in the final report. Mean values of Stance symmetry ratios will be analyzed using repeated measures ANOVA to first compare the relationship of the multiple pre-test measures. If there is no significant difference between the multiple pre-test measures, then the mean of the pre-test measures will be compared to measures at post-test and follow up also using a repeated measures ANOVA. Bonferonni corrections will be used to control for multiple comparisons. The F value and statistical significance will be reported with 95% confidence intervals and effect sizes. A graphical representation of the data will also be reported.

Secondarily, a linear regression model of daily change over time will be created using change scores from the mean of the three Pre Test measures to Day 1 of training. Within day changes for each of the five training days and changes from daily Pre Testing and from daily Post Testing will also be examined with a regression over time. Results of the regression models will be used to determine the presence of a significant change over the course of the intervention and will be reported with the corresponding slope.

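### The slope of within-day change shows whether the session response grows or shrinks, not whether sessions help, yet the SAP counts it as evidence of significant change

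*SAP*

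**What the plan says.** SAP 2.2.2 has two layers for stance symmetry. In the main analysis, once the three Pre-Test visits show no significant difference, "the mean of the pre-test measures will be compared to measures at post-test and follow up also using a repeated measures ANOVA", with Bonferroni correction, effect sizes and 95% confidence intervals.

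The second layer is a set of regressions that the SAP marks as secondary. The opening one models daily change over time and is built "using change scores from the mean of the three Pre Test measures to Day 1 of training". The next sentence adds further series: "Within day changes for each of the five training days and changes from daily Pre Testing and from daily Post Testing will also be examined", again by regression over time. The decision rule for this layer is "Results of the regression models will be used to determine the presence of a significant change over the course of the intervention", and the results "will be reported with the corresponding slope". No intercept or mean within-day change is named, and nothing says which slope answers which question.

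The regression text recurs in 3.2 to 3.7 and is repeated in 3.8. The data exist for every overground gait outcome: the schema in Protocol VI.B lists "10MWT with APDM® before and after training daily", and SAP Table 1 gives time points before the daily treadmill session and after overground training. The Berg Balance Scale, the subject of 3.8, is measured only at Pre-Testing, Post Testing and Follow Up, so it has no daily series.

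For load force, by contrast, SAP 3.1 compares Baseline with same-day Post Training by paired t or Wilcoxon tests. That tests the level of within-day change. The overground outcomes have no counterpart.

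**The concern.** Within-day change is already a difference, post minus pre. Regressing it on day asks whether that difference has a trend. Whether sessions help is a question about its level, which a slope does not address. A training effect that is the same every day leaves nothing for the slope to find. A session effect that is harmful but less so each day gives a positive slope.

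Both patterns are plausible here. Protocol VIII lists muscle fatigue among the expected risks and says any gait benefit is likely to be temporary. The SAP rationale reports that neither earlier study of the device showed transfer to overground gait. The daily post measurement follows 40 minutes of tethered walking, 10 more minutes on the treadmill and 5 to 10 minutes overground.

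At stake is the secondary reading of the daily data for stance symmetry and the other overground gait outcomes. The several slopes may also disagree. If gains are retained but diminishing, the within-day slope is negative while the daily pre and post slopes are positive, and the SAP has no rule for that case.

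**Working it through.** The SAP gives no power, effect size or expected slope for these regressions, so there is no planned figure to reproduce.

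**Inputs from the documents**
- 10 expected completers (Protocol, Participants)
- 5 training days, with gait measured before and after training each day (Protocol VI.B)
- significance level 0.05 (SAP, Statistical Analyses), taken as two-sided
- minimal detectable change of 0.09 for stance symmetry (SAP, Figure 1 text)

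**Assumptions**
- 0.09 is a 95% minimal detectable change, so the per-visit error SD is s = 0.09 / (1.96 × √2) = 0.0325. An alternative of 0.015 is also shown.
- Errors are independent, and every participant has the same true effect.
- Each participant's slope (or mean) is calculated and tested against zero by a one-sample t test with 9 degrees of freedom.
- The effect sizes are illustrative.

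**Slope.** For days 1 to 5 the least-squares slope is Σ(day − 3)·y / 10.
- Constant gain g: g × (−2 − 1 + 0 + 1 + 2) / 10 = 0, whatever g is.
- Gains 0.04, 0.03, 0.02, 0.01, 0: (−0.08 − 0.03 + 0 + 0.01 + 0) / 10 = −0.01 per day, although the mean is +0.02.
- Losses −0.04, −0.03, −0.02, −0.01, 0: +0.01 per day, although the mean is −0.02.

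**Standard errors over 10 participants, s = 0.0325**
- Within-day slope: s × √2 / √10 / √10 = 0.0046
- Daily pre or daily post slope: s / √10 / √10 = 0.00325. Subtracting the Pre-Test mean does not affect the slope.
- Mean within-day change over five days: s × √(2/5) / √10 = 0.0065

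**Rejection rates, s = 0.0325.** Simulation and the noncentral t distribution agree.

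| Scenario | Within-day slope | Daily pre slope | Daily post slope | Mean within-day change |
|---|---|---|---|---|
| +0.02 per session, fully retained | 5% | about 100% | about 100% | 78–79% |
| +0.02 per session, half retained | 5% | 78% | 78% | 78–79% |
| +0.02 per session, lost overnight | about 5% | about 5% | about 5% | about 78% |
| Gains 0.04 falling to 0, retained | 50%, negative | 100%, positive | 98%, positive | 78% |
| Loss shrinking from −0.04 to 0, no carry-over | 49%, positive | 5% | 78%, positive | 78%, negative (correct) |

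For the third row, the mean test has noncentrality 0.02 / 0.0065 = 3.08, which gives 78%. For the last row, the within-day slope has 0.01 / 0.0046 = 2.18, giving 49%, and the daily post slope has 0.01 / 0.00325 = 3.08, giving 78%.

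**Sensitivity, s = 0.015.** The slopes still reject at about 5% when the gain is lost overnight, and the mean test rejects in about 100%. With shrinking fatigue (slope +0.01) the within-day slope is significantly positive in about 99%.

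**Pre-Test mean against Post-Test**, as an uncorrected paired t test at s = 0.0325: a gain lost overnight but present at Post-Test is detected in 33% of trials if it is 0.02 and in about 96–97% if it is 0.05. This comparison stands outside the regressions.

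**The case against.** A reader might infer that effective training would be declared ineffective on the primary stance outcome. The documents do not support that, for three reasons.

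- The decision sentence covers a set of models. The same passage also regresses changes in the daily pre and daily post values. Where gains carry over, those slopes detect them in 98–100% of trials in the fully retained scenarios above.
- The regressions are explicitly secondary. SAP Specific Objective 3 defines the stance question as the Pre-Test mean against Post-Test, and the repeated measures ANOVA answers it whatever the slopes show.
- The SAP speaks of significant change and does not say that a positive slope means benefit. A trend is a fair reading of change over the course of an intervention. Descriptive means, graphs and the planned celeration lines would help to show that the within-day changes were negative.

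All three stand, and they limit the point. They do not remove it: no level test is planned for overground within-day change, no rule assigns a question to each slope, and the whole set is blind to a benefit lost overnight.

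A second tempting reading is that the opening regression is impossible because it has one Day 1 value per participant. Taken literally, such data have no slope. But the sentence also speaks of daily change over time, so a series starting at Day 1 is at least as plausible. This is unclear wording, not a proven error.

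It would also go too far to judge all change from the pre-training series. Its last value precedes session 5, and its slope is likewise zero for a gain lost overnight.

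**Conclusion.** The point holds for the within-day regression and, for the full set of regressions, only in defined circumstances. The within-day slope measures change in session response and cannot show whether sessions help. The full set misses a steady benefit only when gains are not retained overnight: about 5% for each slope against about 78% for the mean within-day change, for a gain of 0.02 per session. With shrinking fatigue and no carry-over, two of the three slopes (within-day at about 49%, daily post at about 78%) are often significantly positive while the average session effect is a loss.

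The algebra needs no assumptions. The percentages rest on 10 completers, on reading 0.09 as a 95% minimal detectable change, on independent errors with a common effect, and on the assumed effect sizes. If the true effect varied between participants, power for a non-zero effect would be lower. The main ANOVA is unaffected, so this is a correction to a secondary analysis that recurs across the overground gait outcomes.

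**What to change.** In SAP 2.2.2 and 3.2 to 3.7:

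- Test each participant's mean within-day change over the five days against zero, with a 95% CI, as the test of session benefit. This mirrors the level test that 3.1 already plans for load force.
- Report the slope of within-day change only as growing or shrinking session response.
- State that the opening regression runs over Days 1 to 5, as change from the Pre-Test mean to each day's pre-training value, and use its slope as the test of carry-over across days.
- State that a positive within-day or daily post slope alone is not read as improvement.
- Keep the ANOVA of Pre-Test mean, Post-Test and Follow Up as the main test of change.

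In 3.8, remove the daily regression text, because the balance scale has no daily measurements.

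The cost is SAP wording and one more secondary test per outcome. No new data are needed.

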### **SPECIFIC OBJECTIVES:**

1) Is this five-day intervention using the TPAD and incorporating faded visual feedback and overground walking feasible in terms of safety, treatment tolerance and adherence in individuals with chronic stroke who present with gait asymmetry?

As a measure of treatment efficacy, this study will specifically address the following questions:

2) Is this treatment paradigm effective at improving load force symmetry over the course of five training sessions as measured from Baseline Day one to Post Training Day five?

3) Is this training paradigm effective to promote transfer and improve stance time symmetry in over ground gait as measured from a mean of the three days in Pre Testing to Post Testing?

The presence of preliminary efficacy in the prior two questions, coupled with measures of safety, treatment tolerance and adherence will be used to answer the over arching question of feasibility and preliminary efficacy.

[figure not shown]

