#### **2. Efficacy**

There will be two primary measures of preliminary efficacy. First, we aim to establish treatment efficacy on the treadmill. Additionally, we aim to determine whether individuals will

be able to transfer gains to improve symmetry in over ground parameters. Specific outcomes are as follows:

**2.1** The primary outcome measure for efficacy of training on the treadmill will be the calculated load force symmetry ratio as measured load force recorded during Baseline and Post Training on the treadmill with embedded force plates.

**2.2** The primary outcome measure for efficacy of transferability will be the stance symmetry ratio calculated from percentage of time in spent in stance phase of the gait cycle. This will be extracted from data provided by APDM® inertial sensors and measured by the mean of the Pre Test visits to Post Testing.

**2.3** Secondary measures of preliminary force efficacy will include within day changes in load force symmetry as taken on the treadmill. As secondary outcomes to evaluate for transfer of the intervention to overground gait, APDM® inertial sensors will be used to record the percentage of time spent in double support, time in swing phase, stride length, and stride velocity. Symmetry ratios will be calculated for percentage of time in swing phase of the gait cycle, and stride length. Gait velocity as a measure of time performing the 10MWT will also be recorded. Lastly, as an additional balance measure, we will also use the total score of the Berg Balance Scale (BBS).

See Table 1 for a detailed list of measures recorded.

Table 1. All outcome variables and time points at which they will be measured.

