## **Statistical Analyses**

Statistical assumptions and normality will be tested prior to running statistical analysis for measures of treatment tolerance, force symmetry, spatiotemporal gait parameters including stance symmetry and balance. A *p value* of 0.05 or lower will be considered statistically significant for all analyses.

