### ***3.2 Swing Symmetry Ratio***

Descriptive statistics (Mean (SD)) will be calculated and reported. Mean values of swing symmetry will be analyzed using repeated measures analysis of variance (ANOVA) to compare the mean of the pre-test measures to measures at post-test and follow up. Bonferonni corrections will be used to control for multiple comparisons. Effect sizes, and 95% confidence intervals will be calculated and reported with the F/Z statistic and p value. A graphical representation of the data will also be reported. Similar to stance symmetry, a linear regression model of daily change over time will be created using change scores from the mean of the three Pre Test measures to Day 1 of training. Within day changes for each of the five training days and changes from daily Pre Testing and from daily Post Testing will also be examined with a regression over time. Results of the regression models will be used to determine the presence of a significant change over the course of the intervention and will be reported with the corresponding slope.

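### Several secondary stance slopes each carry their own significance verdict at 0.05, with no stated correction or governing slope, which leaves an unprotected second route to a claim of change

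*SAP*

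**What the plan says.** SAP section 2 (Efficacy) states "There will be two primary measures of preliminary efficacy"; stance symmetry overground is the second of them. The Specific Objectives put the stance question "as measured from a mean of the three days in Pre Testing to Post Testing", and Efficacy item 2.2 defines the measure the same way.

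SAP 2.2.2 first compares the Pre-Test mean, Post-Test and Follow Up by repeated-measures ANOVA. In that paragraph it says "Bonferonni corrections will be used to control for multiple comparisons". A new paragraph then opens: "Secondarily, a linear regression model of daily change over time will be created using change scores from the mean of the three" Pre-Test measures to Day 1 of training. It continues: "Within day changes for each of the five training days and changes from daily Pre Testing and from daily Post Testing will also be examined", again by regression over time. It closes with their role: "Results of the regression models will be used to determine the presence of a significant change over the course of the intervention".

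The threshold is set once, in the opening of Statistical Analyses: a p value "of 0.05 or lower will be considered statistically significant for all analyses".

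Section 3.2 repeats the block for swing ("Similar to stance symmetry, a linear regression model of daily change over time will be created"). It recurs for double support (3.3), stride length symmetry (3.4), stride length (3.5), stride velocity (3.6) and gait velocity (3.7). It also appears under balance (3.8), although Table 1 schedules the Berg scale only at Pre-Testing, Post Testing and Follow Up. The wording therefore stands in eight places and can apply to seven gait outcomes.

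**The concern.** The regressions are labelled secondary, but they are given a yes/no task: to establish whether significant change occurred over the intervention. That is close to the question the ANOVA answers. With three or more slopes per outcome, each tested at 0.05, the chance that at least one is significant without any effect is above 5%. The SAP does not say which slope counts, whether they must agree, or how to report a significant slope beside a null ANOVA.

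The Specific Objectives use the presence of preliminary efficacy on the two efficacy questions, together with safety, tolerance and adherence, to answer the overall feasibility question. The sample size section says the results will be used to size larger trials. A chance trend reported as a significant change in stance symmetry could therefore colour both uses.

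**Working it through.** The documents state no familywise error rate, so there is no planned figure to reproduce.

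**Inputs from the documents**
- Threshold: 0.05 per analysis. Sidedness is not stated; two-sided is assumed.
- Slopes per outcome: three (within-day change, pre-session, post-session), or four if the opening sentence on change from the Pre-Test mean is a model of its own.
- Number analysed: 10 expected completers of 12 recruited (protocol abstract).
- Training days: 5.

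**Upper reference: independent tests**, 1 − 0.95^k
- Three slopes: 1 − 0.95³ = 0.143
- Four slopes, or three slopes plus the ANOVA: 1 − 0.95⁴ = 0.185

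**Dependence.** The slopes are not independent. With days 1 to 5, a slope is b = Σ(day − 3)·y / 10, since Σ(day − 3)² = 4 + 1 + 0 + 1 + 4 = 10. This is linear in y, so the within-day slope equals the post-session slope minus the pre-session slope. The true rate for three slopes should therefore lie below 14.3%.

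**Null simulation.** 40,000 trials per setting, n = 10, five days. Assumed: same-day pre/post error correlation from 0 to 0.8, and between-participant SD from 0 to 2 times the visit SD. The SAP says only that a linear regression will be used, so three forms were tried. The ANOVA compares the mean of three Pre-Tests, Post-Test and Follow Up.

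| Slope model | Any of 3 slopes | Any of 3 slopes, or the ANOVA |
|---|---|---|
| One slope per participant, one-sample t test | 11.9–12.6% | 15.9–16.7% |
| Least squares on daily group means | 12.7–13.6% | 17.1–18.0% |
| Pooled least squares on all points | 8.2–8.8% | 12.4–13.3% |

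The pooled figures are lower because pre- and post-session changes are measured from each participant's Pre-Test mean. Error in that mean enters the residual variance but not the slope, so those two tests reject only about 2.5–2.8% of the time instead of 5%. A fourth slope raises the first column to about 14–15% (8–10% pooled). Details such as whether Post-Test shares the Day 5 post-session value move the second column by about half a point.

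**Seven gait outcomes.** 7 × 3 = 21 slopes. With participant-level slopes, at least one is significant in about 34–36% of null trials at between-outcome correlation 0.8, 49–50% at 0.5 and 58–61% at 0. The documents give no correlation, so only the range of 34–61% can be stated.

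**The case against.** The strongest reply is that the stance conclusion is already anchored. The Specific Objectives and Efficacy item 2.2 both fix the contrast as Pre-Test mean to Post-Test, and 2.2.2 ranks the regressions as secondary. A reader might infer that a null ANOVA can be overridden by any one slope. No text says so, and that reading should not be pressed. What remains is narrower: the ranking does not remove the significance verdict assigned to the slopes, and nothing stops one from being reported as a significant change.

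A reader might also infer that the three slopes alone give stance a false-positive chance of about 17%. They do not. Three tests at 0.05 reach 14.3% if independent and less here; about 17% requires counting the ANOVA as a further test. Nor can one say that a chance finding somewhere among the seven outcomes is about as likely as not, since that holds only near an assumed correlation of 0.5. The outcomes are clearly related: for each limb, stance and swing percentages are complements, and stride velocity, stride length and walk time overlap.

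Two further points stand in part. The 0.05 rule is a per-test threshold in a small feasibility pilot, and the SAP claims no familywise control, so strict control over secondary trends would be a matter of preference. The scope of the Bonferroni sentence is also not beyond doubt: in 3.2–3.7 it shares a paragraph with the regressions. In every copy, however, it precedes them and follows the ANOVA comparisons, and it is never applied to the slopes explicitly.

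Finally, confidence intervals still show whether zero is excluded. That is true; the change governs what the report may conclude, not what a reader can see.

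**Conclusion.** The point holds as an unprotected second route to a claim of change, not as a failure of the primary stance analysis. For stance with no effect and 10 participants, the chance of at least one significant slope among three is about 12–14% with participant-level or group-mean slopes and 8–9% with pooled least squares. With the ANOVA also counted, it is about 16–18% and 12–13% respectively. Every one of these exceeds 5%, but the exact value depends on a slope model the SAP does not specify and on the assumed error structure. It affects the stance conclusion only if a significant slope is allowed to count as success, which the SAP neither states nor excludes. The point concerns the number of verdicts; how repeated measures within a participant should be modelled is a separate matter. This is a cheap improvement, of low to moderate priority.

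**What to change.** In all eight places (SAP 2.2.2 and 3.2 to 3.8), replace the sentence that gives the regressions a significance verdict with:

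> The slopes are descriptive; they will be reported with 95% confidence intervals and without a significance verdict.

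In 2.2.2 add:

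> The conclusion on stance symmetry rests on the Pre-Test mean to Post-Test comparison.

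The copy in 3.8 must be included, or one verdict sentence would stay in force. No visit, measurement or sample size changes, and every slope that the data allow is still computed and shown. The cost is that the report cannot claim significance from a daily trend.
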